9. DATA COLLECTION

All the data will be collected based on a series of variables which derive from an accurate narrative review of the UI predictors, costs and quality of life of the women affected by the problem (Danforth et al., 2006; Datar et al., 2022; Goren et al., 2014; Harding et al., 2023; Sensoy et al., 2013). These variables are described in Table 1. The obtained information will be gathered in the eCRF, which the investigators will only access during the analyses and synthesis of data.

Table 1 - Outcome and description of the investigated variables

OUTCOME	VARIABLE	DESCRIPTION
UI predictors	Age	The prevalence of UI seems strongly related to the age of the woman and specifically prevalence figures increase with increasing age (Milsom & Gyhagen, 2019)

	Ethnicity	The risk of SUI appears to be lower in black and Asian-American women compared to white women (Danforth et al., 2006; Thom et al., 2006)
	Scholarship	According to some studies (Batmani et al., 2021; Marques et al., 2015), increasing the level of education is an important factor in reducing the incidence of urinary incontinence
	Body Mass Index (BMI)	There is evidence that the prevalence of both UUI and SUI increases proportionately with BMI (Harding et al., 2023)
	Comorbidities	
Lower urinary tract symptoms are associated with multiple comorbid conditions including:
 
 • cardiac failure • chronic renal failure • chronic obstructive pulmonary disease • diabetes • hypertension • metabolic syndrome • pelvic organs prolapse • urinary tract infections • bowel disorders (constipation, irritable bowel syndrome) • sleep disturbances • depression • neurological disease • general cognitive impairment 
(Batmani et al., 2021; Harding et al., 2023; Sensoy et al., 2013; Wang et al., 2010)

	Pelvic or uro-gynecological surgery	Other factors positively associated with SUI include previous pelvic or uro-gynecological surgery (Ellström Engh et al., 2006; Harding et al., 2023)

	Menopause	Menopausal status seems to influence the onset and characteristics of urine leakage (Sensoy et al., 2013; Thangarajah et al., 2020)
	Parity	Pregnancy and childbirth are triggers for SUI (Li et al., 2023; Bortolotti et al., 2000)

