APPENDIX

UI SURVEY – SCHEDA di RACCOLTA DATI

Gentilissima, nel ringraziarla per aver accettato di contribuire a questa ricerca, la invitiamo a rispondere alle domande di seguito, di natura clinica e socio-demografica, con le quali indaghiamo alcuni fattori che potrebbero essere predisponenti all'insorgenza di una condizione nota come incontinenza urinaria.

1. Indichi il suo anno di nascita:

--	--	--	--

2. Indichi la sua nazionalità:

1. Italiana
 2. Straniera (specificare _____)

3. Indichi la regione di domicilio:

- 1. Lombardia
- 2. Altra regione (specificare _____)

4. Se è domiciliata in Lombardia, indichi la provincia del suo domicilio:

 1. Bergamo	 5. Lecco	 9. Monza
 2. Brescia	 6. Lodi	 10. Pavia
 3. Como	 7. Mantova	 11. Sondrio
 4. Cremona	 8. Milano	 12. Varese

5. Indichi il suo peso in chili:

--	--	--

6. Indichila sua altezza in centimetri

10 cm

7. Indichi il grado massimo di studi raggiunto (scolarità):

- 1. Educazione primaria (elementari, medie)
- 2. Educazione secondaria o avanzata (diploma di istituto professionale, tecnico o liceo, laurea)

8. Soffre o ha mai sofferto di una delle seguenti patologie? (Può indicare anche più di una risposta):

- 1. Insufficienza cardiaca
- 2. Insufficienza renale cronica
- 3. Broncopneumopatia cronico-ostruttiva (BPCO)

- 4. Diabete
- 5. Ipertensione
- 6. Sindrome metabolica
- 7. Prollasso vescicale / vaginale / rettale
- 8. Infezione ricorrente delle vie urinarie
- 9. Sindrome da intestino irritabile
- 10. Stipsi
- 11. Disturbi del sonno
- 12. Depressione
- 13. Patologia neurologica
- 14. Disabilità cognitiva generale
- 14. Altro (specificare: _____)

9. Ha mai subito interventi di chirurgia ginecologica e/o urologica?

- 1. Sì
- 2. No

10. Se alla domanda precedente ha risposto Sì, specifichi quale/i intervento/i ha subito:

11. In quale stato menopausale si definirebbe?

- 1. In pre-menopausa
- 2. A inizio menopausa
- 3. In post-menopausa

12. Ha figli?

- 1. Sì
- 2. No

13. Se alla domanda precedente ha risposto Sì, indichi il numero di figli:

- 1
- 2
- ≥ 3

14. Indichi l'anno di nascita dell'ultimo figlio

--	--	--	--

15. Quanti parto per via vaginale ha avuto?

- 0
- 1
- 2
- ≥ 3

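### Survey questions 8 and 9 do not match three predictors listed in Table 1: uterine prolapse is not named, infection is limited to recurrent, and other pelvic surgery is never asked about

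*Protocol*

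**What the plan says.** Protocol section 9, Table 1, lists among the UI predictors "pelvic organs prolapse" and "urinary tract infections" (both under comorbidities), and "previous pelvic or uro-gynecological surgery" as a predictor of its own. It gives no case definition for any of them.

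Section 9.1 says the survey content rests on the Table 1 variables. Section 9.1.1 assigns the predictors to survey questions 1–23, while noting that the survey covers only part of the variable list.

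In the Appendix, question 8 asks about conditions a woman has now or has ever had. It allows several answers. Option 7 is "Prollasso vescicale / vaginale / rettale" and option 8 is "Infezione ricorrente delle vie urinarie". The list ends with an open "Altro (specificare" field. Question 9 is a yes/no item: "Ha mai subito interventi di chirurgia ginecologica e/o urologica". Question 10 asks for details, but only after a yes.

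Section 7.2 excludes women with urinary and gynaecological surgery, and the recruitment interview in section 8 asks patients and caregivers about past gynaecological surgery. Identifying predictors is expected result (c) in section 5, and their association with UI is a secondary outcome in section 4.

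**The concern.** Question 8 follows the comorbidity list of Table 1 almost item by item, so its departures look unintended, and the Protocol does not explain them.

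Naming three prolapse sites invites a woman who has been told that she has uterine prolapse to think the box is not meant for her. A woman with a single infection finds no box, although the Table 1 term would include her. A woman who has had pelvic surgery that is neither gynaecological nor urological should answer no to question 9 and is then recorded as having had none.

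If such women end up in the unexposed group, three things follow: the predictor's frequency is understated, the exposed group shrinks, and the odds ratio moves towards 1. An exposure that was not asked about cannot be derived later, whatever the analysis plan says. The data are anonymous (section 16), so returning to respondents is not foreseen. The pilot in 13 women is reported as checking clarity, discomfort and completion time, not agreement with Table 1.

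**Working it through.** **Step 1: texts side by side**

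| Predictor | Table 1 | Form | Gap | Way to record it anyway |
|---|---|---|---|---|
| Prolapse | any pelvic organ | Q8 option 7: bladder, vagina, rectum | uterus not named | tick option 7 regardless, or write it in the open field |
| Infection | urinary tract infections, unqualified | Q8 option 8: recurrent only | non-recurrent infection | open field |
| Surgery | pelvic or uro-gynaecological | Q9: gynaecological and/or urological | other pelvic surgery | none: no other option, and Q10 opens only after a yes |

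**Step 2: effect of exclusion 7.2 on the surgery item.** The Table 1 surgical exposure has two parts: uro-gynaecological surgery and other pelvic surgery. If 7.2 is applied, the first part is removed from the sample and question 9 is answered no by nearly everyone. The second part stays eligible, but no item asks about it. The surgery predictor then has no usable contrast.

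**Step 3: illustration of size.** The Protocol gives no figure to reproduce: no exposure frequency, no effect size and no capture rate. The assumed inputs are exposure prevalence π = 0.10, UI risk in the unexposed p0 = 0.30, true odds ratio 2.0, a captured share s of exposed women of 0.8, 0.6 or 0.4, no false positives, and capture unrelated to UI. The 30% lies within the 25–45% that section 11 reports for most studies.

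- Risk in the exposed: odds = 2 × 0.30/0.70 = 0.857, so p1 = 0.857/1.857 = 0.4615.
- Recorded exposure: e = π·s. Recorded unexposed: u = 1 − e.
- Risk in the recorded unexposed: pu = [π(1−s)p1 + (1−π)p0]/u.
- Observed odds ratio: 0.857 / [pu/(1−pu)].
- Variance of the log odds ratio, times N: V = 1/[e·p1(1−p1)] + 1/[u·pu(1−pu)].

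Full capture: V = 1/(0.10 × 0.2485) + 1/(0.90 × 0.21) = 40.24 + 5.29 = 45.53.

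| s | Recorded exposure | pu | Observed OR | V | SE ratio √(V/45.53) |
|---|---|---|---|---|---|
| 0.8 | 8% | 0.3035 | 1.97 | 50.30 + 5.14 = 55.44 | 1.10 |
| 0.6 | 6% | 0.3069 | 1.94 | 67.06 + 5.00 = 72.07 | 1.26 |
| 0.4 | 4% | 0.3101 | 1.91 | 100.60 + 4.87 = 105.46 | 1.52 |

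The shortcut 1/√s gives 1.12 to 1.58. It is slightly too high because it ignores the variance from the unexposed group.

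**Step 4: range for other assumptions.** With a true odds ratio of 2.0 and p0 from 10% to 45%, the same formula gives:

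| Exposure | s = 0.7 | s = 0.3 |
|---|---|---|
| 5–10% | 1.94–1.98 | 1.88–1.95 |
| 50% | 1.65–1.71 | 1.44–1.51 |

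Dilution becomes material only when the exposure is common and much of it is missed.

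**The case against.** A reader might infer that exposed women are certain to be filed as unexposed. The form does not support that for prolapse and infection. Question 8 takes several answers and has an open field, and a woman with uterine prolapse who ticks option 7 is coded correctly. The error arises only if she ticks nothing, or if her free text is not coded to the listed condition. Nothing in the Protocol shows how often either would happen, so this objection stands.

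Table 1 lists the predictors with a literature rationale and does not define them, so the form can be read as the operational definition. Under a question about lifetime history, limiting infection to recurrent infection is defensible. This also stands: for infection, what is left is a disagreement between two labels.

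A reader might also argue that an infection within the four-week symptom window should have its own box, with a prevalence estimate that leaves those women out. The Protocol nowhere proposes recent infection as something to adjust for or set aside. That would be a new design element, not the repair of an error.

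On surgery, it can be said that 7.2 governs the item, so that simply widening question 9 would mix excluded and eligible operations in one answer. That is right about the remedy, but it does not remove the gap: Table 1 names pelvic surgery, and question 9 has no place for it.

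Finally, the effect is limited to three of many secondary predictors, and the dilution is small for uncommon exposures. Both statements are correct.

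**Conclusion.** The concern holds as a mismatch between Table 1 and the form that creates a risk of under-recording. It does not hold as proven misclassification. The surgery gap is the firmest part, because other pelvic surgery has no place in question 9 and is the only Table 1 surgical exposure left once 7.2 is applied. The prolapse gap depends on how respondents read a list of three sites and on how free text is coded. The infection gap is an unreconciled label.

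The primary prevalence estimate is untouched. For an uncommon predictor the cost is mainly in recorded frequency and precision. On the assumed inputs, a 10% exposure is recorded as 4–8%, an odds ratio of 2.0 becomes about 1.91–1.97, and the standard error grows by a factor of about 1.10–1.52. The 40–80% capture is purely an assumption and does not apply to question 9, where other pelvic surgery is not captured at all. The larger dilution at 50% exposure would matter only if any infection ever were the intended predictor, which the Protocol does not settle.

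**What to change.** Before the paper and REDCap forms are used:

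1. Reword question 8 option 7 as *Prolasso degli organi pelvici (utero, vescica, vagina, retto)*.
2. Ask about other pelvic surgery (for example bowel or rectum) as a separate yes/no item. Do not merge it into question 9, so that it stays distinct from the surgery named in 7.2.
3. Reconcile the surgery predictor in Table 1 with exclusion 7.2, and state which surgical exposure is to be analysed.
4. Make Table 1 and option 8 agree on whether the predictor is any or recurrent urinary infection.
5. State that open-field answers naming a listed condition are coded to that condition.

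The cost is one more short item, a few wording edits and a few seconds per respondent. Items 1 and 2 cannot be repaired at analysis, so they should come first.

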4. OUTCOMES

Primary outcome

- Prevalence of middle-aged women with urinary incontinence.

Secondary outcomes

- Description of UI and related predictors, quality of life, social impact and costs.
- Association between UI and related predictors, quality of life, social impact and costs.

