7. INCLUSION/EXCLUSION CRITERIA

7.1 Inclusion criteria

- Female sex
- Middle age (40-65 years old)
- Informed consent signed
- Comprehension of written and spoken Italian language
- Female outpatients intended for any hospital unit (outpatient clinic, day surgery and day hospital patients included) and every female caregiver respecting the previous inclusion criteria, recruited at the central admission and at the private admission of the four hospitals involved
- Female workers (healthcare professionals and administrative personnel) of the four hospitals

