9.1.1 UI Survey

A survey, written in Italian by the authors, will collect women's socio-demographic, economic and clinical characteristics, based on the variables reported in Table 1. The entire survey is attached in Appendix.

 
I.R.C.C.S. Ospedale San Raffaele
	
STUDY PROTOCOL
	
WUIPS Version n. 1 23.08.2023

---	------------------------------	---

A total of 29 questions will attempt to acquire information about some of the previously defined variables: specifically, 23 questions will be related to socio-demographic and clinical predictors of UI (n. 1-23), one question will be about the onset of the UI symptomatology (n. 35), one question about sexuality (n. 36) and four questions will investigate the direct and indirect costs of UI (n. 37-40). The survey was tested as a pilot on a sample of 13 women aged between 40 and 65 years old and was assessed as suitable for the following aspects: understanding and clarity of the questions, absence of questions that put the participant in difficulty, completion time (which resulted maximum of 5 minutes).

9.1.2 International Consultation of Incontinence Modular Questionnaire Urinary Incontinence Short Form (ICIQ UI-SF)

The International Consultation of Incontinence Modular Questionnaire Urinary Incontinence Short Form (ICIQ UI-SF) is a questionnaire that allows the assessment of the prevalence, frequency, and perceived cause of UI and its impact on everyday life. It is an appropriate scale for estimating national prevalence in representative samples (Bedretdinova et al., 2015).

ICIQ UI-SF was developed and validated in English for the first time by Avery and colleagues in 2004, and then Tubaro and colleagues made an Italian Validation in 2006. This last version will be used in the study.

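### Question 11 has women assign their own menopausal stage from three undefined labels, with no item to reclassify them, so its association with UI risks bias of unknown size and direction

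*Protocol*

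**What the plan says.** Protocol section 9, Table 1, lists menopause among the UI predictors with the rationale "Menopausal status seems to influence the onset and characteristics of urine leakage". The table does not define the stages. Section 4 makes the predictors part of a secondary outcome: "Association between UI and related predictors, quality of life, social impact and costs". Section 7.1 admits women aged 40 to 65.

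The variable is collected by one item in the Appendix, question 11: "11. In quale stato menopausale si definirebbe". The answers offered are "1. In pre-menopausa", "2. A inizio menopausa" and "3. In post-menopausa" (options 1, 2 and 3 below). The form explains none of them and has no box for a woman who does not know.

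On testing, section 9.1.1 states: "The survey was tested as a pilot on a sample of 13 women aged between 40 and 65 years old". That test looked at clarity, discomfort and completion time, which was at most five minutes.

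**The concern.** A stage variable is useful only if women with the same history land in the same category. Here the woman supplies the definition herself. Options 2 and 3 are not clearly separate, since the start of menopause and the time after it share the first years after the last period. The transition has no box of its own and can be read into option 1 or option 2.

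The age range runs from women who still cycle regularly to women long past menopause, so respondents near these boundaries are to be expected. If they sort themselves by personal understanding, the estimate for option 2 describes no identifiable group, and the contrast of option 3 with option 1 compares groups of unknown make-up. A larger sample does not cure this, and no analysis plan can recover facts that the form never asked for.

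**Working it through.** The protocol gives no effect size, error rate or sample size for this association, so there is no figure to reproduce. The check has two parts: what the form could recover, and an illustration of how the bias can move.

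**1. Can stage be recovered from other items?**
- Question 1 (year of birth) gives age, not stage.
- Questions 12 to 16 cover children and deliveries. The year of the last birth can expose a gross inconsistency, no more.
- Question 40 asks about treatment, but only for leakage, and continent women are told to skip it.
- Nothing asks about the last period, cycle regularity or hormone use.
- Sections 8 and 16 describe anonymous collection, so re-contact cannot be relied on.

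Stage therefore cannot be rebuilt.

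**2. What could option 2 contain?** Assumed: 20% of women in the transition, half of whom tick option 2; 45% post-menopausal, of whom a share q tick option 2. The post-menopausal share of option 2 is 0.45q / (0.10 + 0.45q):
- q = 0.10: 0.045/0.145 = 31%
- q = 0.25: 0.1125/0.2125 = 53%
- q = 0.40: 0.18/0.28 = 64%

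**3. Which way do the odds ratios move?** Assumed true shares: 40% pre, 20% early, 40% post. Assumed UI prevalence: 25%, 35% and 45%, chosen within the 25–45% that section 11 cites for most studies. True odds ratios against pre:
- early (0.35/0.65)/(0.25/0.75) = 1.62
- post (0.45/0.55)/(0.25/0.75) = 2.45

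| Assumed error | Early OR | Post OR |
|---|---|---|
| None | 1.62 | 2.45 |
| 30% error between neighbouring classes, unrelated to UI | 1.54 | 2.24 |
| 30% exchange between early and post only, unrelated to UI | 1.97 | 2.28 |
| 20% of incontinent pre-menopausal women tick option 2 | 2.60 | 3.07 |

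The third row in full:
- option 2 holds 0.20×0.70 + 0.40×0.30 = 0.26 of women, with UI in 0.20×0.70×0.35 + 0.40×0.30×0.45 = 0.103, that is 39.6%; the odds ratio is (0.103/0.157)/(1/3) = 1.97
- option 3 holds 0.34, with UI in 0.147; the odds ratio is (0.147/0.193)/(1/3) = 2.28

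If the early class truly does not differ from pre (25%, 25%, 45%), 30% error between neighbours creates an early odds ratio of 1.37 where the truth is 1.00.

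**4. Does the answer depend on what option 1 means?** Assumed: 35% regular cycles, 20% transition, 45% post; UI prevalence 20%, 30%, 30%; half of the transition women tick option 1.
- UI prevalence in option 1: (0.07 + 0.03)/0.45 = 22.2%
- Observed post-versus-option-1 odds ratio: (0.30/0.70)/(0.222/0.778) = 1.50
- True value if option 1 means regular cycles only: (0.30/0.70)/(0.20/0.80) = 1.71
- True value if it means everyone before menopause: prevalence (0.07 + 0.06)/0.55 = 23.6%, odds ratio 1.38

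The same answers are too low under one meaning and too high under the other. The form does not say which applies.

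**The case against.** The best defence is that self-reported stage is a reasonable economy in a short survey, with several safeguards. Section 7.2 excludes women with gynecological surgery, which should remove most surgical menopause and hysterectomy, where self-staging is hardest. Patients and caregivers meet a researcher at recruitment, and section 10 says that data collectors are trained nurses and midwives, so a label can be queried. The pilot found the questions clear. Age is available for adjustment. Table 1 claims only that status seems to matter, as one predictor among many.

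Much of this stands, and it limits the importance of the point. It does not remove the defect. The surgery exclusion does nothing for the natural transition or for bleeding altered by drugs. Staff complete the form through an emailed link, with no interviewer described. A pilot in 13 women on clarity does not show that women with the same history tick the same box. Adjusting for age does not restore stage.

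A reader might infer two stronger things. The first is that regularly cycling women have no answer. They do: option 1, read literally, means before menopause and includes them. The difficulty is that they share it with some transition women. The second is that the association is bound to be diluted. The document gives no error rate, and the illustrations above move odds ratios both ways.

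**Conclusion.** The point holds as a weakness of measurement in one predictor. Question 11 is the sole source for menopausal status, its labels are undefined and not clearly separate, and nothing else in an anonymous survey allows correction. The menopause-UI association is at risk of misclassification bias whose size and direction the document does not determine, and an estimate for option 2 would have no clear meaning.

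Every share, stage-specific prevalence and error rate used above is an assumption. The results show how the bias can behave; they do not predict it. When the assumed error was unrelated to UI, the post-versus-pre contrast moved modestly (2.45 to 2.24 or 2.28 at 30%). The middle category was less stable, and error related to UI inflated both contrasts. The effect is confined to a secondary outcome, and the primary prevalence is untouched. This is a cheap improvement worth making before data collection.

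**What to change.** Before launch, replace question 11, on paper and in RedCap, with a factual item on the last period:
- within the past 3 months, with the usual rhythm
- within the past 12 months, but irregular
- more than 12 months ago, with the year
- don't know

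Add one tick for periods absent or altered because of hormones or another treatment. State in the protocol the rule that derives stage from these answers: regular, transition, post-menopausal or unclassifiable.

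The cost is one reworded item and one added tick, a few seconds more per respondent, and a small unclassifiable group to be reported as such. If collection has already begun, describe the variable as self-perceived status and do not interpret option 2 as a defined stage.

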UI prevalence and symptomatology	Lifestyle factors	
 Unhealthy voiding behavior (Hu and Pierre, 2019) and low physical activity may contribute to UUI onset (Li et al., 2023) Smoking cessation is a general public health measure and has been shown to be weakly associated with improving urgency, frequency and UI (Danforth et al., 2006; Harding et al., 2023) Decrease in fluid intake may improve some symptoms in patients with SUI and idiopathic detrusor overactivity (Swithinbank et al., 2005) Reduction of caffeine intake may reduce symptoms of frequency and urgency (Harding et al., 2023) An association was seen between alcohol consumption and urinary incontinence in middle-aged and older women (Lee & Hirayama, 2012)
	Frequency of urine leakage	To assess the severity of UI among female, we need measuring the “frequency” and “usual amount” of leakage ranged from “moderate” to “strong” (Avery et al., 2004)
	Perceived quantity of urine leakage	
	Type of urine leakage	It is focused on subtypes of urinary incontinence (SUI, UUI and MUI) (Abrams et al., 2003)
	Time of onset of urine leakage	The mean age in which urine leakage begins seems to be lower for SUI compared to MUI and UUI (Thangarajah et al., 2020)

 
I.R.C.C.S. Ospedale San Raffaele
	
STUDY PROTOCOL
	
WUIPS Version n. 1 23.08.2023

---	------------------------------	---

UI quality of life, social impact	General interference with daily life	The measurement of UI should incorporate the impact that the condition may have on quality of life (Avery et al., 2004)
	Interference with specifical activities	
Specifically:
 
 • Physical Activity • Social Relationships • Travel • Emotional Health 
(Monticone et al., 2021; Shumaker et al., 1994)

	Interference with sexual life	Some articles report that UI affects sexual aspects of the individual (Felsted & Supiano, 2019; Marques et al., 2015). According to other studies, sexual activity does not seem to be damaged by UI (Siracusano et al., 2003)
Costs	Work productivity	UI imposes a high economic burden because of work productivity loss (Goren et al., 2014)
	Weekly costs of hygiene care products	UI is associated with substantial routine care “costs” (Subak et al., 2006)

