9.1 Instruments

Three instruments will be employed to collect data, as reported in Table 2.

 I.R.C.C.S. Ospedale San Raffaele	STUDY PROTOCOL	WUIPS Version n. 1 23.08.2023
--	-----------------------	--

Table 2 - Instruments employed in the study

Instrument	Data of interests
UI Survey	Women's socio-demographic and clinical characteristics based on the variables reported in Table 1
Italian version of the International Consultation of Incontinence Modular Questionnaire Urinary Incontinence Short Form (ICIQ UI-SF) (Tubaro et al., 2006)	Prevalence and symptomatology of UI (Bedretdinova et al., 2015)
Italian version of the Incontinence Impact Questionnaire-7 (IIQ-7) (Monticone et al., 2020)	Impact on life of urinary incontinence among women (Shumaker et al., 1994)

A survey, written in Italian by the authors and tested on a sample of 13 women between 40 and 65 years old, will collect socio-demographic, economic and clinical characteristics of all the female participants included in the study. The requested data will be based on the variables reported in Table 1.

The Italian version of the International Consultation of Incontinence Modular Questionnaire Urinary Incontinence Short Form (ICIQ UI-SF) will be used to investigate UI symptoms in women (Avery et al., 2004; Tubaro et al., 2006).

The Italian version of the Incontinence Impact Questionnaire-7 will be used to assess the impact of UI on women's quality of life (Monticone et al., 2021; Shumaker et al., 1994).

The materials necessary for data collection will be included in a paper module for patients and caregivers and online for staff (see attachment). Each subject included will fill in the module which will be transmitted to the Promoter with the appropriately anonymized data. Given the growing need for digital data management in clinical trials and in compliance with current regulatory requirements, researchers will independently set up the eCRF (electronic Case Report Form), via the RedCap platform.

In each hospital center involved in the study, a nurse will be identified, as the contact person of the Center, who will be responsible for supervising the appropriate recording of data and compliance with this research protocol.

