16. Quanti parto cesarei ha avuto?

- 0
- 1
- 2

□ > 3

17. Pratica attività fisica in maniera frequente?

18. Fuma o ha mai fumato?

1. Attuale fumatore 2. Ex fumatore 3. Mai fumatore

19. Se fuma o fumava, quante sigarette al giorno consuma/consumava?

1-5 > 10-20
 > 5-10 > 20

20. Quanti caffè assume in media al giorno?

0 2
 1 3

21. Quanti drinks alcolici assume in media a settimana?

 0	 15-21
 1-7	 ≥ 22
 8-14	

22. Quanta acqua beve in media al giorno?

- 1. Meno di $\frac{1}{2}$ litro
- 2. Tra $\frac{1}{2}$ litro e un litro
- 3. Più di un litro, fino a un litro e $\frac{1}{2}$
- 4. Più di un litro e $\frac{1}{2}$

23. Quante volte al giorno svuota la vescica mediamente?

- 1. Ogni ora o più frequentemente
- 2. Ogni due-tre ore circa
- 3. Ogni quattro ore o meno frequentemente

ICIQ-UI Short Form (Italian)

A molte persone capita, a volte, di avere delle perdite di urina. Stiamo tentando di determinare quante persone abbiano delle perdite di urina e quanto ciò costituisca, per loro, un problema. Le saremmo grati se rispondesse alle seguenti domande facendo riferimento a come si è sentita, in media, nelle ULTIME QUATTRO SETTIMANE.

24. Con quale frequenza le capita di avere delle perdite di urina? (faccia una crocetta su una sola casella)

- 1. Mai
- 2. Una volta la settimana o meno
- 3. Due tre volte la settimana

- 4. Circa una volta al giorno
- 5. Più volte al giorno
- 6. Continuamente

25. Ci piacerebbe sapere qual è, secondo lei, la quantità di urina che perde. Quanta urina le capita di perdere di solito (sia quando indossa una protezione che quando non la indossa)? (faccia una crocetta su una sola casella)

- 1. Per niente
- 2. Una piccola quantità
- 3. Una discreta quantità
- 4. Una notevole quantità

26. In generale, in che misura le perdite di urina hanno interferito con la sua vita quotidiana? La preghiamo di fare un cerchietto attorno ad un numero tra 0 (per niente) e 10 (moltissimo)

0 1 2 3 4 5 6 7 8 9 10

per niente

moltissimo

27. In che occasione le capita di avere delle perdite di urina? (Indichi, tra le seguenti, tutte le situazioni che corrispondono al suo caso)

- 1. Mai – non ho perdite di urina
- 2. Ho perdite di urina prima di riuscire a raggiungere il bagno
- 3. Ho perdite di urina in occasione di colpi di tosse o starnuti
- 4. Ho perdite di urina quando sono addormentata

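### Questions 20 and 22 record only coffee and water, although Table 1 bases these lifestyle predictors on caffeine and fluid intake

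*Protocol*

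**What the plan says.** In section 9, the lifestyle row of Table 1 gives the reasons for collecting these exposures. On caffeine it says "Reduction of caffeine intake may reduce symptoms of frequency and urgency". On fluid it says "Decrease in fluid intake may improve some symptoms in patients with SUI and idiopathic detrusor overactivity". Section 9.1 ties the survey to that table: "The requested data will be based on the variables reported in Table 1". Section 9.1.1 is a little looser: "A total of 29 questions will attempt to acquire information about some of the previously defined variables".

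The survey in the Appendix has one item for each exposure:

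- Question 20: "20. Quanti caffè assume in media al giorno", with boxes that read 0, 1, 2 and 3 in the available text.
- Question 22: "22. Quanta acqua beve in media al giorno", in four bands, the last being anything above one and a half litres.

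The only other beverage item is question 21, "21. Quanti drinks alcolici assume in media a settimana", which records alcohol and ends in an open category (≥ 22).

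Section 5 lists the identification of UI predictors among the expected results, and section 4 makes the association between UI and its predictors a secondary outcome. The primary outcome is prevalence.

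**The concern.** Coffee is one source of caffeine and water is one source of fluid. No item asks about tea, cola, energy drinks or the total volume of drinks, and none separates decaffeinated coffee. Women with substantial caffeine or fluid intake from other sources therefore enter the data as zero or low and are mixed into the comparison group.

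The gap would be easy to miss in the results, because both exposures will look measured. It also cannot be repaired at analysis. Sections 8 and 16 describe anonymous data from a single completion of the form, and the protocol provides no way to go back to participants. What is at stake is how two secondary associations are read.

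**Working it through.** The protocol states no figure that depends on these items, so there is nothing of its own to reproduce. The check is a comparison of texts, followed by an illustration on assumed inputs.

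**1. Exposure in Table 1 against item on the form**

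| Exposure in the Table 1 rationale | Item on the form | Not recorded |
|---|---|---|
| Caffeine intake | Question 20: coffees per day | Tea, cola, energy drinks; decaffeinated coffee not separated |
| Fluid intake | Question 22: water per day | All other non-alcoholic drinks; alcohol is in question 21, as drinks per week and not as volume |

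Both items are narrower than the exposure they stand for, and no other item fills the gap.

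**2. Top response categories**

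- Questions 13 and 15: ≥ 3, open.
- Question 16: > 3, open.
- Question 19: > 20, open.
- Question 21: ≥ 22, open.
- Question 22: above one and a half litres, open.
- Question 20: 3, closed as it reads here.

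Question 20 is the only exception, and the text around it is damaged. Question 16 runs 0, 1, 2, > 3 where its twin, question 15, ends in ≥ 3, and question 17 has lost its answer boxes. A lost ≥ sign in question 20 is plausible, so a closed scale is not established.

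**3. Illustration of the effect on an association**

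Every input here is an assumption; none comes from the protocol. Take 100 women, 40 with truly high exposure, a UI risk of 36% with high and 26% with low exposure, and a share m of the high-exposure women recorded as low whatever their UI status. The recorded-high group then contains only truly exposed women and keeps a risk of 36%.

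Risk in the recorded-low group = (60 × 0.26 + 40m × 0.36) / (60 + 40m)

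- m = 30%: (15.6 + 4.32) / 72 = 19.92 / 72 = 27.7%. Observed difference 36 − 27.7 = 8.3 points.
- m = 50%: (15.6 + 7.2) / 80 = 22.8 / 80 = 28.5%. Observed difference 36 − 28.5 = 7.5 points.

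The true difference is 36 − 26 = 10 points, so 83% and 75% of it remain. The illustration shows the direction and a modest loss. It does not estimate the loss in this study.

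**The case against.** The strongest reply has four parts.

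*Table 1 does not list caffeine or fluid as variables.* This is correct as to form. The variable is the broad lifestyle entry, and the caffeine and fluid sentences stand in the description column as literature background. A reader might infer that the protocol promises to measure total caffeine and total fluid; it never says so. What stands is that these sentences are the stated reason for asking, and that questions 20 and 22 are the only items that can serve it.

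*Section 9.1.1 promises only some of the variables.* This does not settle the matter. Other Table 1 variables are covered by the two validated questionnaires (questions 24–34), which explains the qualifier. Caffeine and fluid are not covered there.

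*The response scales are adequate.* A reader might infer that high intakes have no box. For water this is wrong, since the top band of question 22 is open. For coffee it is unproven, for the reason given in the working. Even read literally, a woman who drinks four coffees and ticks 3 stays in the highest category.

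*The consequence is small.* Largely true. These are 2 of 23 predictor items, they feed a secondary aim, and short proxies suit a form that the pilot found to take at most 5 minutes. But that pilot, in 13 women, looked at clarity, discomfort and completion time. It did not test whether the items capture the intended exposure.

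**Conclusion.** The mismatch is real and limited. The form measures coffee and water where the stated rationale concerns caffeine and fluid, so women whose intake comes from other drinks are recorded as unexposed or low. If that misrecording is unrelated to UI, it will tend to weaken the two associations. If women with leakage change what they drink, the direction is less certain. The size cannot be derived from the protocol, and the 8.3 and 7.5 points above rest wholly on assumed inputs.

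A reader might go further and infer that a null finding could not be told apart from mismeasurement. The protocol does not support this, and the illustration speaks against it: even with half of the exposed women misrecorded, three quarters of the difference remains.

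The primary prevalence estimate does not use these items. This is a cheap improvement to a secondary aim.

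**What to change.** Reword question 20 to ask for the daily number of caffeinated drinks (coffee, tea, cola, energy drinks), with an open top category. Reword question 22 to ask for total daily fluids from all drinks; its existing open top band is sufficient in form.

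If the items are kept, for instance because the form is already in use, label and report the exposures as coffee and water, and draw no conclusion on caffeine or total fluid.

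In either case, check on the original form whether the last box of question 20 is ≥ 3, and open it if it is not.

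The cost is small. Both items belong to the researchers' own survey, so neither validated questionnaire is touched and no question is added. Totals across drinks are slightly harder to recall than coffees or water alone, and the new wording needs a brief recheck of clarity because it replaces piloted text.
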